7.1 Adverse Event Collection in the Case Report Forms

Version 09/11/2025 page 31 of 63

All adverse events that occur beginning with start of treatment (minus exceptions defined in Section 6.0) must be captured in the Toxicity Form. Baseline AEs should be captured on the Medical History Form.

Participant death due to disease progression should be reported on the Toxicity Form as grade 5 disease progression. If death is due to an AE (e.g. cardiac disorders: cardiac arrest), report as a grade 5 event under that AE. Participant death must also be recorded on the Death Form.

8 MEASUREMENT OF EFFECT

8.1 Antitumor Effect – RECIST 1.1

For the purposes of this study, patients should be re-evaluated for response at the specified times in section 5.3.4.

Response and progression will be evaluated in this study using the new international criteria proposed by the revised Response Evaluation Criteria in Solid Tumors (RECIST) guideline (version 1.1) [Eur J Ca 45:228-247, 2009]. Changes in the largest diameter (unidimensional measurement) of the tumor lesions and the shortest diameter in the case of malignant lymph nodes are used in the RECIST criteria.

8.1.1 Disease Parameters

Measurable disease: Measurable lesions are defined as those that can be accurately measured in at least one dimension (longest diameter to be recorded) as >20 mm by chest x-ray, as >10 mm with CT scan, or >10 mm with calipers by clinical exam. All tumor measurements must be recorded in millimeters (or decimal fractions of centimeters).

Malignant lymph nodes: To be considered pathologically enlarged and measurable, a lymph node must be >15 mm in short axis when assessed by CT scan (CT scan slice thickness recommended to be no greater than 5 mm). At baseline and in follow-up, only the short axis will be measured and followed.

Non-measurable disease: All other lesions (or sites of disease), including small lesions (longest diameter <10 mm or pathological lymph nodes with ≥10 to <15 mm short axis), are considered non-measurable disease. Bone lesions, leptomeningeal disease, ascites, pleural/pericardial effusions, lymphangitis cutis/pulmonitis, inflammatory breast disease, and abdominal masses (not followed by CT or MRI), are considered as non-measurable.

Note: Cystic lesions that meet the criteria for radiographically defined simple cysts should not be considered as malignant lesions (neither measurable nor non-measurable) since they are, by definition, simple cysts.

Version 09/11/2025 page 32 of 63

'Cystic lesions' thought to represent cystic metastases can be considered as measurable lesions, if they meet the definition of measurability described above. However, if non-cystic lesions are present in the same patient, these are preferred for selection as target lesions.

Target lesions: All measurable lesions up to a maximum of 2 lesions per organ and 5 lesions in total, representative of all involved organs, should be identified as target lesions and recorded and measured at baseline. Target lesions should be selected on the basis of their size (lesions with the longest diameter), be representative of all involved organs, but in addition should be those that lend themselves to reproducible repeated measurements. It may be the case that, on occasion, the largest lesion does not lend itself to reproducible measurement in which circumstance the next largest lesion which can be measured reproducibly should be selected. A sum of the diameters (longest for non-nodal lesions, short axis for nodal lesions) for all target lesions will be calculated and reported as the baseline sum diameters. If lymph nodes are to be included in the sum, then only the short axis is added into the sum. The baseline sum diameters will be used as reference to further characterize any objective tumor regression in the measurable dimension of the disease.

Non-target lesions: All other lesions (or sites of disease) including any measurable lesions over and above the 5 target lesions should be identified as non-target lesions and should also be recorded at baseline. Measurements of these lesions are not required, but the presence, absence, or in rare cases unequivocal progression of each should be noted throughout follow-up.

8.1.2 Methods for Evaluation of Measurable Disease

All measurements should be taken and recorded in metric notation using a ruler or calipers. All baseline evaluations should be performed as closely as possible to the beginning of treatment and never more than 4 weeks before the beginning of the treatment.

The same method of assessment and the same technique should be used to characterize each identified and reported lesion at baseline and during follow-up. Imaging-based evaluation is preferred to evaluation by clinical examination unless the lesion(s) being followed cannot be imaged but are assessable by clinical exam.

Clinical lesions: Clinical lesions will only be considered measurable when they are superficial (e.g., skin nodules and palpable lymph nodes) and ≥ 10 mm diameter as assessed using calipers (e.g., skin nodules). In the case of skin lesions, documentation by color photography, including a ruler to estimate the size of the lesion, is recommended.

Version 09/11/2025 page 33 of 63

Conventional CT and MRI: This guideline has defined measurability of lesions on CT scan based on the assumption that CT slice thickness is 5 mm or less. If CT scans have slice thickness greater than 5 mm, the minimum size for a measurable lesion should be twice the slice thickness. MRI is also acceptable in certain situations (e.g. for body scans).

Use of MRI remains a complex issue. MRI has excellent contrast, spatial, and temporal resolution; however, there are many image acquisition variables involved in MRI, which greatly impact image quality, lesion conspicuity, and measurement. Furthermore, the availability of MRI is variable globally. As with CT, if an MRI is performed, the technical specifications of the scanning sequences used should be optimized for the evaluation of the type and site of disease. Furthermore, as with CT, the modality used at follow-up should be the same as was used at baseline and the lesions should be measured/assessed on the same pulse sequence. It is beyond the scope of the RECIST guidelines to prescribe specific MRI pulse sequence parameters for all scanners, body parts, and diseases. Ideally, the same type of scanner should be used and the image acquisition protocol should be followed as closely as possible to prior scans. Body scans should be performed with breath-hold scanning techniques, if possible.

PET-CT: At present, the low dose or attenuation correction CT portion of a combined PET-CT is not always of optimal diagnostic CT quality for use with RECIST measurements. However, if the site can document that the CT performed as part of a PET-CT is of identical diagnostic quality to a diagnostic CT (with IV and oral contrast), then the CT portion of the PET-CT can be used for RECIST measurements and can be used interchangeably with conventional CT in accurately measuring cancer lesions over time. Note, however, that the PET portion of the CT introduces additional data which may bias an investigator if it is not routinely or serially performed.

Ultrasound: Ultrasound is not useful in assessment of lesion size and should not be used as a method of measurement. Ultrasound examinations cannot be reproduced in their entirety for independent review at a later date and, because they are operator dependent, it cannot be guaranteed that the same technique and measurements will be taken from one assessment to the next. If new lesions are identified by ultrasound in the course of the study, confirmation by CT or MRI is advised. If there is concern about radiation exposure at CT, MRI may be used instead of CT in selected instances.

Endoscopy, Laparoscopy: The utilization of these techniques for objective tumor evaluation is not advised. However, such techniques may be useful to confirm complete pathological response when biopsies are obtained or to determine relapse in trials where recurrence following complete response (CR) or surgical resection is an endpoint.

Version 09/11/2025 page 34 of 63

Tumor markers: Tumor markers alone cannot be used to assess response. If markers are initially above the upper normal limit, they must normalize for a patient to be considered in clinical complete response. Specific guidelines for both CA-125 response (in recurrent ovarian cancer) and PSA response (in recurrent prostate cancer) have been published [JNCI 96:487-488, 2004; J Clin Oncol 17, 3461-3467, 1999; J Clin Oncol 26:1148-1159, 2008]. In addition, the Gynecologic Cancer Intergroup has developed CA-125 progression criteria which are to be integrated with objective tumor assessment for use in first-line trials in ovarian cancer [JNCI 92:1534-1535, 2000].

Cytology, Histology: These techniques can be used to differentiate between partial responses (PR) and complete responses (CR) in rare cases (e.g., residual lesions in tumor types, such as germ cell tumors, where known residual benign tumors can remain).

The cytological confirmation of the neoplastic origin of any effusion that appears or worsens during treatment when the measurable tumor has met criteria for response or stable disease is mandatory to differentiate between response or stable disease (an effusion may be a side effect of the treatment) and progressive disease.

FDG-PET: While FDG-PET response assessments need additional study, it is sometimes reasonable to incorporate the use of FDG-PET scanning to complement CT scanning in assessment of progression (particularly possible 'new' disease). New lesions on the basis of FDG-PET imaging can be identified according to the following algorithm:

- Negative FDG-PET at baseline, with a positive FDG-PET at follow-up is a sign of PD based on a new lesion.
- No FDG-PET at baseline and a positive FDG-PET at follow-up: If the positive FDG-PET at follow-up corresponds to a new site of disease confirmed by CT, this is PD. If the positive FDG-PET at follow-up is not confirmed as a new site of disease on CT, additional follow-up CT scans are needed to determine if there is truly progression occurring at that site (if so, the date of PD will be the date of the initial abnormal FDG-PET scan). If the positive FDG-PET at follow-up corresponds to a pre-existing site of disease on CT that is not progressing on the basis of the anatomic images, this is not PD.
- FDG-PET may be used to upgrade a response to a CR in a manner similar to a biopsy in cases where a residual radiographic abnormality is thought to represent fibrosis or scarring. The use of FDG-PET in this circumstance should be prospectively described in the protocol and supported by disease-specific medical literature for the indication. However, it must be acknowledged that both approaches may lead to false positive CR due to limitations of FDG-PET and biopsy resolution/sensitivity.

Version 09/11/2025 page 35 of 63

Note: A 'positive' FDG-PET scan lesion means one which is FDG avid with an uptake greater than twice that of the surrounding tissue on the attenuation corrected image.

8.1.3 Response Criteria

8.1.3.1 Evaluation of Target Lesions

Complete Response (CR): Disappearance of all target lesions. Any pathological lymph nodes (whether target or non-target) must have reduction in short axis to <10 mm.

Partial Response (PR): At least a 30% decrease in the sum of the diameters of target lesions, taking as reference the baseline sum diameters.

Progressive Disease (PD): At least a 20% increase in the sum of the diameters of target lesions, taking as reference the smallest sum on study (this includes the baseline sum if that is the smallest on study). In addition to the relative increase of 20%, the sum must also demonstrate an absolute increase of at least 5 mm. (Note: the appearance of one or more new lesions is also considered progressions).

Stable Disease (SD): Neither sufficient shrinkage to qualify for PR nor sufficient increase to qualify for PD, taking as reference the smallest sum diameters while on study.

8.1.3.2 Evaluation of Non-Target Lesions

Complete Response (CR): Disappearance of all non-target lesions and normalization of tumor marker level. All lymph nodes must be non-pathological in size (<10 mm short axis).

Note: If tumor markers are initially above the upper normal limit, they must normalize for a patient to be considered in clinical complete response.

Non-CR/Non-PD: Persistence of one or more non-target lesion(s) and/or maintenance of tumor marker level above the normal limits.

Progressive Disease (PD): Appearance of one or more new lesions and/or unequivocal progression of existing non-target lesions. Unequivocal progression should not normally trump target lesion status. It must be representative of overall disease status change, not a single lesion increase.

Although a clear progression of "non-target" lesions only is exceptional, the opinion of the treating physician should prevail in such circumstances, and

Version 09/11/2025 page 36 of 63

the progression status should be confirmed at a later time by the review panel (or Principal Investigator).

8.1.3.3 Evaluation of Best Overall Response

The best overall response is the best response recorded from the start of the treatment until disease progression/recurrence (taking as reference for progressive disease the smallest measurements recorded since the treatment started). The patient's best response assignment will depend on the achievement of both measurement and confirmation criteria.

For Patients with Measurable Disease (i.e., Target Disease)

1 of 1 defents with wiedsufuble Discuse (nei, 1 diget Discuse)						
Target	Non-Target	New	Overall	Best Overall Response		
Lesions	Lesions	Lesions	Response	when Confirmation is		
				Required*		
CR	CR	No	CR	>4 wks. Confirmation**		
CR	Non-CR/Non-	No	PR			
	PD					
CR	Not evaluated	No	PR	\ \ \ \ \ \ \ \ \ \ \ \ \ \ \ \ \ \ \		
PR	Non-CR/Non-	No	PR	>4 wks. Confirmation**		
	PD/not					
	evaluated					
SD	Non-CR/Non-	No	SD	Documented at least once		
	PD/not			>4 wks. from baseline**		
	evaluated			24 wks. Holli baselille		
PD	Any	Yes or	PD			
		No				
Any	PD***	Yes or	PD	no prior SD, PR or CR		
		No				
Any	Any	Yes	PD			

^{*} See RECIST 1.1 manuscript for further details on what is evidence of a new lesion.

Note: Patients with a global deterioration of health status requiring discontinuation of treatment without objective evidence of disease progression at that time should be reported as "symptomatic deterioration." Every effort should be made to document the objective progression even after discontinuation of treatment.

For Patients with Non-Measurable Disease (i.e., Non-Target Disease)

Non-Target Lesions	New Lesions	Overall Response
CR	No	CR
Non-CR/non-PD	No	Non-CR/non-PD*
Not all evaluated	No	not evaluated
Unequivocal PD	Yes or No	PD

Version 09/11/2025 page 37 of 63

^{**} Only for non-randomized trials with response as primary endpoint.

^{***} In exceptional circumstances, unequivocal progression in non-target lesions may be accepted as disease progression.

Any	Yes	PD			
* 'Non-CR/non-PD' is pr	referred over 'stable disease	e' for non-target disease			
since SD is increasingly used as an endpoint for assessment of efficacy in					
some trials so to assign th	is category when no lesion	s can be measured is not			
advised					

8.1.3.4 Duration of Response

Duration of overall response: The duration of overall response is measured from the time measurement criteria are met for CR or PR (whichever is first recorded) until the first date that recurrent or progressive disease is objectively documented (taking as reference for progressive disease the smallest measurements recorded since the treatment started).

The duration of overall CR is measured from the time measurement criteria are first met for CR until the first date that progressive disease is objectively documented.

Duration of stable disease: Stable disease is measured from the start of the treatment until the criteria for progression are met, taking as reference the smallest measurements recorded since the treatment started, including the baseline measurements.

9 DATA AND SAFETY MONITORING

In compliance with the Washington University Institutional Data and Safety Monitoring Plan, the Principal Investigator will provide a Data and Safety Monitoring (DSM) report to the Washington University Quality Assurance and Safety Monitoring Committee (QASMC) semi-annually.

. The first report is required either 30 days after the enrollment of the 5th participant (if sooner than 6 months after study activation) or 6 months after study activation (provided at least one patient has been enrolled; if zero patients have been enrolled at the 6-month mark, the first report will be required one year after accrual opens provided at least one patient has been enrolled).

The Principal Investigator will review all patient data at least monthly and provide a semi-annual report to the Quality Assurance and Safety Monitoring Committee (QASMC). This report will include:

- Study demographic information (local protocol number, protocol title, list of primary study team members, study sites, primary and secondary sponsors, IND/IDE status, date of most recent QA audit, and study status and history (including activation and suspension dates)
- Accrual information, including study-wide target accrual and actual accrual, anticipated and/or actual accrual end date, and accrual by year by site (if applicable)
- Subject status information presented in both cumulative format (total number of subjects who consented, enrolled, screen failed, started intervention, discontinued

Version 09/11/2025 page 38 of 63

- intervention, went off study, expired) and current format (number of subjects in screening, on intervention, in follow-up, or off study at time of report)
- Protocol objectives and the number of participants who are evaluable for each objective
- History of study (including summaries of substantive amendments, accrual suspensions and reasons, protocol exceptions, errors, and breaches of confidentiality)
- Summary of exceptions, noncompliance reports, and unanticipated problems reported to the IRB
- Early stopping rules and data describing whether the stopping rules have been met (if applicable)
- Interim analysis plans and the results of the interim analysis (if applicable)
- Separate SAE and worst grade toxicity tables, each separated by site (if applicable) and arm/cohort/dose level (if applicable)
- Participant-level response and survival data by arm/cohort/dose level (if applicable)
- Summary of specimen collection (percentage of participants who have had specimens collected at each required time point)
- Abstract submissions/publications
- Summary of any recent literature that may affect the safety of participants or the ethics of the study

•

The study principal investigator and Research Patient Coordinator will monitor for serious toxicities on an ongoing basis. Once the principal investigator or Research Patient Coordinator becomes aware of an adverse event, the AE will be reported to the HRPO and QASMC according to institutional guidelines.

10 STASTISTICAL CONSIDERATIONS

10.1 Phase I Methodology for Primary Endpoint

10.1.1 Background of TITE-CRM and trial rules

The Time-to-Event Continual Reassessment Method (TITE-CRM) proposed by Cheung and Chappell is an adaptive Phase I design (98). In a TITE-CRM clinical trial, patients enroll as they become available to be studied. Each participant is assigned to a dose level from a set of dose levels pre-defined by investigators and is monitored for DLTs over time. The design is adaptive in that the dose level assigned to a newly enrolled patient depends on the dose level assignments and dose limiting toxicity outcomes of the patients already in the study. A patient's observation period ends at the occurrence of a DLT or, if a DLT does not occur, after a fixed time T of follow-up. The trial ends when a fixed number of patients, n, have been observed. Once the final patient has been observed, the MTD can be estimated using the available data.

Version 09/11/2025 page 39 of 63

The TITE-CRM differs from the traditional CRM in that the estimation process is weighted to account for the proportion of the observation period that each currently enrolled patient has been observed. By not requiring complete observation before the enrollment of the next patient, new participants can be assigned a dose and begin evaluation as they become available, subsequently shortening the overall duration of the study.

The Biostatistics Unit at the University of Michigan Comprehensive Cancer Center has developed a program titecrm.sas for SAS 9 (SAS Institute, Inc.; Cary, NC) that makes all of the calculations necessary to determine dose allocation of a trial in real-time. They have also developed simulation programs that allow the user to determine the efficacy of the trial based on *a priori* estimates of the probabilities of toxicity and necessary sample sizes.

In order to properly utilize this type of trial, a few assumptions and many rules must be determined before the start of the trial. The main assumption that must be determined is how many different dose levels will be included in the trial and *a priori* estimates of the probability of a DLT at each of those dose levels. For this trial, we have 5 dose levels listed below $(d_1,...,d_5)$, with initial toxicity probability estimates $(p_1,...,p_5)$ ranging from 0.05 to 0.25, respectively. The following table shows the dose design with associated estimated probabilities of toxicity.

Dose Level	Number of	PTV	PTV	PTV	PTV
	fractions of	Dose/fx	Total	Standard	EQD2
	IMPT	(Gy)	Dose	BED (Gy_{10})	
			(Gy)		
-1	5	5	25	37.50	31.25
1	5	6	30	48.00	40.00
Starting					
Level					
2	5	7	35	59.50	49.58
3	5	8	40	72.00	60.00

10.1.2 TITE-CRM design

The starting dose can have a large impact on the properties of the design. After the trial is completed, most information about the MTD will be obtained if many patients are treated at or near the MTD. Thus, the sooner the choice of dose can converge on the MTD the more effective the trial will be. However, due to the uncertainty of the MTD in the reirradiation of locoregionally recurrent rectal cancer, we will start at the two dose levels lower than the expected MTD to prioritize safety. Therefore, our starting dose for this trial will be PTV total dose of 30 Gy.

The next thing to be considered is the dose escalation rules. For this trial, we will only allow a single dose level escalation per new patient enrolled on the trial.

Version 09/11/2025 page 40 of 63

Therefore, if the previous patient was treated at dose level, d_k , then a new patient can only be treated at dose levels d_{k+1} or lower. In order to determine at which level to treat the new patient, we will use a weighted, cumulative time of exposure approach.

The total length of follow-up for DLT for any patient is 6 months from the start of radiation therapy. In order to efficiently and effectively determine the MTD, we allow for a dose change when the cumulative time of exposure is 6 months. Additionally, since previously published data shows that most toxic events occur within the first 6 months from start of treatment, we also implement a linear weighting function wherein the first 6 months accounts for 75% of the follow-up where the last 3 months attributes 25% of the follow-up information. The dose for the next patient is selected so that the estimated probability at that dose is close to the target level.

A feature of the dose escalation part of the TITE-CRM program is the flexibility in specifying the margin for the dose selection. This allows the selection of the dose level for the next patient that may have an estimated probability of toxicity larger than the target level but less than the target level plus the margin. It finds the dose closest to the target probability even if it has a higher estimated probability. For this trial we set the admissible margin to be 5%, therefore, the MTD will be chosen as the dose that yields a posterior toxicity estimate closest to 35% while being between 30% and 40%. The admissible margin is also used to help determine stopping rules for the trial.

In order to account for the possibility of poor initial outcomes we will employ a run-in of 6 patients, meaning that the minimum number of treated patients will be 6. If after these 6 patients, or any other time during the trial, the lowest dose level has a posterior probability higher than 40% then the trial will stop.

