3	5	8	40	72.00	60.00

Note – the first 6 evaluable patients enrolled will be treated at Dose Level 1 Please refer to section 10.0

Version 09/11/2025 page 10 of 63

SCHEDULE OF ACTIVITIES

	Screening	Pre- treatment ⁸	Radiation	1-2 Weeks post RT	6-8 Weeks post RT	3 Mo post RT ¹	6 Mo post RT ¹	9 Mo post RT ¹	12 Mo post RT ¹	
Informed consent	X^2									
H&P / PS / weight / DRE ¹³	X^2		X^3	X	X	X	X	X	X	
MRI pelvis ⁴	X^2				X	5	X	X	X	
CT chest / abdomen / pelvis with contrast ⁶	X^2				X ⁶		X	X	X	
Endoscopy ⁷	X^2				X	15				
OPTIONAL biopsy	$X^{2, 15}$				Х	ζ				
CBC w/diff	X^2	X^2			X^9		X			
CMP	X^2	\mathbf{X}^2			X^9		X			
CEA		X			X^9		X			
SCCA		X			X ⁹		X			
CRP		X			X ⁹		X			
LDH		X			X ⁹		X			
Pregnancy test	$X^{10,11}$									
Radiation therapy			X^{12}							
EORTC QLQ-C30		X		X		X	X	X	X	
EORTC QLQ-C29		X		X		X	X	X	X	
Adverse events		X	X^3	X	X	X	X	X	X	

- 1. +/- 2 weeks
- 2. No more than 60 days prior to registration. Screening and baseline labs can be the same draw provided the timing aligns.
- 3. Performed once during radiation therapy.
- 4. Cross-sectional imaging with either MRI or CT is acceptable.
- 5. MRI pelvis and CT chest/abdomen with contrast may be obtained 6 weeks to 3 months after radiation completion with a RECIST read at 3 months only.
- 6. If PET/CT scan is done, then CT chest/abdomen/pelvis not required.
- 7. Endoscopy with colonoscopy, sigmoidoscopy, or proctoscopy will be performed if feasible after screening.
- 8. Baseline labs and QOL assessments should be performed within 30 days of radiation therapy.
- 9. Labs should be drawn once 6 weeks to 3 months after radiation completion but should be drawn before surgery if the patient undergoes salvage surgery.
- 10. Mandatory for women of childbearing potential.
- 11. Within 14 days of registration.
- 12. 5 fractions over 1 week.
- 13. DRE only to be done if feasible.15. OPTIONAL endoscopy with biopsy performed 6 weeks to 3 months after completion of RT; for research purposes only.
- 15. OPTIONAL screening biopsy to be performed at time of baseline SOC endoscopy.

Version 09/11/2025 page 11 of 63

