1.7.2 Scientific Rationale for Study Design

The standard phase I 3+3 dose-escalation design is poorly suited for trials of radiotherapy, for which toxicities may occur up to several months after treatment. In this case, the 3+3 design, or any design that requires all patients to have completed observation for toxicity, is subject to openings and closings as patients present after a dose level potentially has filled, but before sufficient time has elapsed to be certain that treatment has not produced dose-limiting toxicities (DLT).

As such, dose escalation for this trial will be guided by the Time-to-Event Continual Reassessment Method (TITE-CRM). TITE-CRM seeks to determine the target dose, defined as the dose most closely identified with the target rate, which is the largest acceptable probability of toxicity, determined a priori by the investigators based on the relative costs and benefits of the treatment (typically between 5% and 25%). As the trial progresses and patients do or do not experience toxicities at different doses, the estimates of probability of toxicity are recalculated using a Bayesian expectation, and subsequent patients are assigned to doses under the principle to always treat at the target dose.

In a Monte Carlo simulation of 60,000 phase I trials comparing 3+3 design to TITE-CRM in studies with delayed toxicity, the TITE-CRM trials were significantly shorter when toxicity observation times are long, treated more patients at or above the maximum-tolerated dose, identified the MTD more accurately, but did not expose patients to significant additional risk (97). Additionally, given that TITE-CRM concentrates most of the accrual around the target dose, early estimates of efficacy are possible.

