10.2.1 Workflow

The first patient will be enrolled on the trial and treated at PTV total dose 30 Gy, which is one dose level below the hypothesized MTD. That patient will be entered into the titecrm.sas program and follow-up will begin from start of treatment.

For the purposes of this trial, the patient will be followed from start of treatment until the patient completes 12months of follow-up, has a DLT, or is lost to follow-up. If any of these endpoints occur, the statistician will be notified and the date corresponding to the event will be entered into the program. While there is a maximum follow-up of 6 months for observation of possible toxicities, sometimes patients have a delay in their treatment resulting in the need for a prolonged observation period. This delay will be accounted for, as needed, for this study to ensure a complete 6-month follow-up.

When a new patient is enrolled on the trial, the statistician will be notified of the date of enrollment. At that time the statistician will update the follow-up for all patients currently on the trial and determine the dose that will be administered for the new patient. We will utilize the cumulative time of exposure method, which will allow the contribution of patients with no DLT at this time to be partially weighted consistent with their time observed. We will also utilize the weight function to place more emphasis on the first 6 months follow-up (75% weight) compared to the last 3 months of follow-up (25% weight). At this point, the program provides a summary of the number of patients treated at each dose so far, along with the number of DLTs that have occurred. The posterior probability and 95% credible intervals of dose limiting toxicity for each dose level is calculated. At this point, the model determines the dose level that has an estimated toxicity rate closest to 35% within the 5% admissible margin.

The newly enrolled patient will be enrolled in the corresponding dose level if that dose level is within one dose level from the dose level the most current patient is enrolled on. If the suggested dose level is more than one dose level from the current dose level the next patient will be enrolled on the dose level that is closest to the current level in the direction of the dose level determined from the estimated

Version 09/11/2025 page 42 of 63

posterior probability. This continues until the trial has accrued all 20 patients or, if after 6 patients are enrolled, the estimated posterior.

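### The 6-month exposure condition names no dose level and the workflow does not apply it, so 40 Gy can open after one briefly observed 35 Gy patient

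*Combined protocol and SAP*

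**What the plan says.** Section 10.1.2 sets two limits on escalation. One is the step size: "we will only allow a single dose level escalation per new patient enrolled on the trial", judged against the level of the previous patient. The other is exposure: "we allow for a dose change when the cumulative time of exposure is 6 months". The exposure sentence names no dose level, no set of patients and no minimum number of patients.

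Section 10.2.1 describes what the statistician does at each enrolment. It uses the same term for something else: "We will utilize the cumulative time of exposure method, which will allow the contribution of patients with no DLT" to be partially weighted by time observed. The model's dose is then assigned "if that dose level is within one dose level from the dose level the most current patient is enrolled on". No 6-month threshold appears there.

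The remaining brakes are the Schema note that "the first 6 evaluable patients enrolled will be treated at Dose Level 1" and a stopping rule (10.1.2 and Appendix F) that looks only at the lowest dose. Section 5.2 refers back to Section 10. Nothing written sets a minimum follow-up or number of patients at 35 Gy before 40 Gy may be given.

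**The concern.** The exposure condition is the only written rule that could make the trial wait for information at one dose before moving to the next, and its meaning is open. If exposure is pooled over the trial, the run-in at 30 Gy satisfies it before escalation starts and it never acts again. If 10.2.1 is followed as written, there is no condition at all. In both cases the only limit on reaching 40 Gy is one level per new patient, however briefly the latest patient has been observed.

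This matters because Section 1.7.2 chose the design on the ground that "toxicities may occur up to several months after treatment". The patients are being reirradiated, Section 1.7.3 acknowledges that organ tolerance is not yet known for such schedules, and the DLT list includes fistula, perforation and necrosis. The top dose could open on one or two patient-months at the dose below.

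**Working it through.** **The plan's own figures.** Section 10.2 reports about 95% of simulated trials completing and the MTD at the third to fifth level in 89%. These cannot be reproduced, because the model, prior, true DLT rates and accrual rate are not given. The counting rule used in the dose-finding program is not shown either.

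**Inputs from the plan.** 20 patients in 36 months of recruitment, so one every 36/20 = 1.8 months. DLT window 6 months. First six patients at 30 Gy. Target 35%, margin 30–40%. Initial estimates 0.25, 0.30, 0.35 and 0.40 at 25, 30, 35 and 40 Gy (table in 10.2).

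**Assumptions.** Power model, p(dose) = (initial estimate)^exp(a), with a normal with mean 0 and variance 0.5 or 1.34. A DLT-free patient followed t months has weight w = min(t/6, 1) and contributes 1 − w·p to the likelihood. A DLT contributes p.

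**Step 1: pooled exposure when patient 7 enters.** With even accrual and follow-up capped at 6 months, the six run-in patients contribute 6 + 6 + 6 + 5.4 + 3.6 + 1.8 = 28.8 patient-months. A pooled 6-month condition is already met and stays met.

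**Step 2: the dose for patients 7 and 8.** At patient 8 the single 35 Gy patient is DLT-free with weight 1.8/6 = 0.30.

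| Run-in result | Estimate at 40 Gy, patient 7 | Estimate at 40 Gy, patient 8 |
|---|---|---|
| 1 DLT in 6 (first or sixth patient) | 33–37% | 30–33% |
| 0 DLT in 6 | 13% (variance 1.34) or 20% (0.5) | 11% or 18% |

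With one DLT, 40 Gy is the level closest to 35% at both decisions. The step limit holds patient 7 at 35 Gy. Patient 8 gets 40 Gy, and the estimate is inside the margin, so the written rule applies without interpretation. With no DLT, no dose is inside the margin, and escalation also assumes that the closest dose is used. With two DLTs in six there is no escalation.

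**Step 3: what one short observation can show.** If the true 35 Gy rate were 35%, with DLT times uniform over 6 months, the chance of seeing a DLT within 1.8 months is 0.35 × 1.8/6 = 0.105, about 10%.

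**Step 4: counting at the current level.** With even accrual, exposure at 35 Gy is 1.8 patient-months when patient 8 enters, 3.6 + 1.8 = 5.4 at patient 9, and 5.4 + 3.6 + 1.8 = 10.8 at patient 10. So 40 Gy opens after three 35 Gy patients instead of one.

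**Step 5: simulation.** 1000 trials per setting, the same random numbers for both rules, exponential gaps with mean 1.8 months, DLT times uniform on 0–6 months, closest dose used. True DLT rates at 25/30/35/40 Gy were .05/.10/.20/.35, .10/.20/.35/.55, .25/.30/.35/.40 and .05/.10/.15/.25. Ranges cover all four curves and both variances.

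| Measure | Pooled | Current level |
|---|---|---|
| Of trials reaching 40 Gy, share after one 35 Gy patient | 73–93% | 1–2% |
| Median patient-months at 35 Gy before first 40 Gy patient | 1.4–1.8 | 9.4–9.9 |
| Median patients given 40 Gy before 35 Gy has 6 patient-months | 2–3 | 0 |

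Current-level counting gave 0.05–0.24 fewer DLTs per trial (0.4–0.6 fewer at 40 Gy, partly offset at lower levels). The chance of choosing the level closest to 35% changed by −1 to +3 points.

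**Sensitivity (variance 1.34, 500 trials per run).** The pooled share reaching 40 Gy after one 35 Gy patient was 80–90% with the plan's 6+3-month weights, and 63–70% if the dose is held when none is inside the margin.

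**The case against.** The strongest reply is that the pooled reading makes the sentence in 10.1.2 idle after the run-in, so counting at the current dose is the more natural meaning. Section 10.2.1 does name the cumulative exposure method, and a procedural summary that omits a threshold does not cancel it. The program may already count this way. That is possible, but it is not written, and a statistician who follows 10.2.1 exactly would apply no threshold.

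A second reply is that acting on partial follow-up is the purpose of TITE-CRM. That is correct, and the design does not require complete observation. But the sponsor chose to add an exposure condition, and a condition that is added needs a defined meaning.

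Third, the contrast between 73–93% and 1–2% largely restates the rule being imposed and is not evidence of patient benefit. The outcome measures move little, and the percentages rest on a model, prior, true rates and DLT timing that the plan does not give. This stands. The case for change is better observation before first exposure to the top dose, not fewer DLTs on average or a better MTD.

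**Conclusion.** The concern holds. Under the pooled reading, or the workflow as written, 40 Gy can open at patient 8 after one 35 Gy patient observed for under two months. This does not depend on a favourable run-in: it also happens with one DLT in six, where the 40 Gy estimate of 30–33% is inside the plan's margin. A current-level reading would prevent it, but the plan does not state that reading.

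The size of the effect rests on the power model, the two prior variances, accrual of one patient per 1.8 months and uniform DLT timing. The emptiness of a pooled condition after the run-in rests only on the accrual rate. This should be fixed, because the first exposures to the highest reirradiation dose are at issue and the correction is cheap. It does not threaten the MTD estimate.

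**What to change.** State in both 10.1.2 and 10.2.1:

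> The dose may be increased only when patients treated at the current dose level have at least 6 months of cumulative DLT follow-up, each counted up to 6 months. This is checked at each enrolment. De-escalation is never delayed.

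Use a different term in 10.2.1 for the partial weighting, such as follow-up weighting. Confirm that the dose-finding program applies the same rule. Re-run the 10.2 simulation with it, and report patients and patient-months at each level before the next opens.

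The cost is a few sentences and a simulation re-run. The first 40 Gy patient comes about two enrolments later (median patient 10–11 instead of 8), and 0.9–1.7 fewer of the 20 patients are treated at 40 Gy. Accrual does not pause, because new patients enter at the current level meanwhile.
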